## 5.5 Sample size

Our primary null hypothesis ( $H_0$ ) is that the NR-induced increases in cerebral NAD levels (measured by P-MRS), or NRRP expression (measured by FDG-PET) are not dose-responsive. The alternative hypothesis ( $H_A$ ) is that at least one of these measures will be dose responsive. In the NADPARK study, all three measures showed a highly significant increase in the group receiving 1000 mg NR ( $n = 15$ ) compared to the placebo group ( $n = 15$ ). In the NADPARK study, treatment with 1000mg of NR led to an increase in cerebral NAD-levels by a factor of 1.27 from baseline in the treatment group, whereas the change in the placebo group was negligible at -0.43%. Under the  $H_A$ , we assume that cerebral NAD levels will increase in a linear fashion in the 2000 mg NR and 3000 mg NR groups, respectively. Based on these assumptions and given a type I error rate of 5% ( $\alpha = 0.05$ ) and a type II error rate of 10% ( $\beta = 0.1$ , power = 90%), we estimated that a sample size of 30 individuals will be required in the dose escalation group. Accounting for drop-out and statistical safety margin, we estimate that the study requires 40 subjects in this group.

For the secondary outcomes, we assume that the metabolomic analyses will have sufficient power, since they produced very large effect sizes and highly significant results in the NADPARK study with 15 individuals per group.

## 6 Safety Analyses

General safety evaluations will be based on the incidence, intensity, and type of AEs, and clinically significant changes in the patient's physical examination findings, vital signs, and clinical laboratory results. Only AE grade 2 and above will be recorded. Safety variables will be tabulated and presented for all patients in the safety set.

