### 8.1 Definitions

#### 8.1.1 Adverse Event (AE)

An AE is any untoward medical occurrence in a patient administered a pharmaceutical product and which does not necessarily have a causal relationship with this treatment.

An adverse event (AE) can therefore be any unfavorable and unintended sign (including an abnormal laboratory finding), symptom, or disease temporally associated with the use of an investigational product, whether or not related to the investigational product.

The term AE is used to include both serious and non-serious AEs.

If an abnormal laboratory value/vital sign is associated with clinical signs and symptoms, the sign/symptom should be reported as an AE and the associated laboratory result/vital sign should be considered as additional information that must be collected on the relevant CRF.

Only intensity 2 and 3 is registered as AE in eCRF, see section 8.3. An AE has to interfere with everyday life to be of intensity 2 or 3.

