**The intensity of the adverse event: Only intensity grade 2 and 3 is registered as AE in eCRF .**

Assessment of Intensity

The investigator will make an assessment of intensity for each AE and SAE reported during the study and assign it to 1 of the following categories:
 
 
Mild: An event that is easily tolerated by the participant, causing minimal discomfort and not interfering with everyday activities, and or requires clinical or diagnostic observations.
 
Moderate: An event that causes sufficient discomfort to interfere with normal everyday activities, and or requires medical intervention.
 
Severe: An event that prevents normal everyday activities. An AE that is assessed as severe should not be confused with an SAE. Severe is a category utilized for rating the intensity of an event; and both AEs and SAEs can be assessed as severe.
 

The Causal relationship of the event to the study medication will be assessed as one of the following:

- **Unrelated:** There is not a temporal relationship to investigational product administration (too early, or late, or investigational product not taken), or there is a reasonable causal relationship between non-investigational product, concurrent disease, or circumstance and the AE.
- **Unlikely:** There is a temporal relationship to investigational product administration, but there is not a reasonable causal relationship between the investigational product and the AE.
- **Possible:** There is reasonable causal relationship between the investigational product and the AE. Dechallenge information is lacking or unclear.
- **Probable:** There is a reasonable causal relationship between the investigational product and the AE. The event responds to dechallenge. Rechallenge is not required.
- **Definite:** There is a reasonable causal relationship between the investigational product and the AE.
- It will be recorded in the eCRF the outcome of the adverse event, the action taken and whether the event is resolved or still ongoing.

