- It is important to distinguish between serious and severe AEs. Severity is a measure of intensity whereas seriousness is defined by the criteria in Section 8.1. An AE of severe intensity need not necessarily be considered serious. For example, nausea that persists for several hours may be considered severe nausea, but is not an SAE. On the other hand, a stroke that results in only a limited degree of disability may be considered a mild stroke, but would be an SAE.

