## 8.4 Reporting Procedure

### 8.4.1 AEs and SAEs

All adverse events and serious adverse events that should be reported as defined in section 8.1.1 will be recorded in the patient's CRF.

SAEs must be reported by the investigator to the sponsor, (coordinating investigator: [name] or PI [name], see contact information) within 24 hours after the site has gained knowledge of the SAE. Every SAE must be documented by the investigator on the SAE pages to be found in e-CRF. The initial report shall promptly be followed by detailed, written reports if necessary. The initial and follow-up reports shall identify the trial subjects by unique code numbers assigned to the latter.

The sponsor keeps detailed records of all SAEs reported by the investigators and performs an evaluation with respect to seriousness, causality and expectedness.

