### **2.1.1 Safety laboratory (blood)**

All safety laboratory parameters will be collected at the timepoints as indicated in the Flow Chart (page 47), and include hematology, liver enzymes/parameters, clinical chemistry, thyroid status. The samples will be analyzed at the local laboratory at the study site. The respective reference ranges must be provided to the central study administration for uploading into the eCRF.

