### 6.1 Adverse Events

#### 6.1.1 Descriptive Statistics

The frequency and severity of adverse events (AE) will be presented in tabular format between all three randomization groups and NR dose levels (1000 mg, 2000 mg and 3000 mg). AEs are evaluated as being either unrelated, unlikely, possible, probable or definite in relation to the investigational medicinal product (IMP). AEs will be grouped by status; Moderate or Severe and grouped by relation to the IMP. AEs will be presented by number and by percentage of group. The safety analysis set (SAS) will be used for analysis. The variables are continuous. No further statistical testing will be performed on the AEs. We refer the reader to the study protocol for a more detailed definition of AE severity and registration procedures.

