### 6.2 Clinical Laboratory Parameters

Safety clinical laboratory parameters were collected and assessed, both to be used to identify adverse events and for exploratory analyses. Clinical laboratory parameters will be summarised by treatment group and visit.

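### The SAP's safety tables have no serious-event category and no count of out-of-range laboratory values, and the protocol gives two different thresholds for a Moderate adverse event

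*SAP*

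**What the plan says.** **Recording rule.** SAP section 6: "Only AE grade 2 and above will be recorded". Protocol 8.1.1 applies the same filter to AE registration in the eCRF. The same section uses the term AE for both serious and non-serious events, counts an abnormal laboratory finding as an AE, and adds: "An AE has to interfere with everyday life to be of intensity 2 or 3".

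**Intensity scale.** Protocol 8.3 defines Moderate as "An event that causes sufficient discomfort to interfere with normal everyday activities, and or requires medical intervention". It then separates intensity from seriousness with an example: "a stroke that results in only a limited degree of disability may be considered a mild stroke, but would be an SAE".

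**SAEs.** Protocol 8.4.1 says "All adverse events and serious adverse events that should be reported as defined in section 8.1.1 will be recorded" in the CRF, and goes on to require that every SAE be documented on the SAE pages. Protocol 8.5 has AEs and SAEs discussed in the main results and in the safety part of the Clinical Study Report.

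**Planned AE tables.** SAP 6.1.1 tabulates AEs across the three arms and the three NR dose levels: "AEs will be grouped by status; Moderate or Severe and grouped by relation to the IMP". The safety row of SAP 4.5 lists number and severity of AEs. The body of the SAP does not mention SAEs; the term appears only in its abbreviation list.

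**Laboratory.** SAP section 6 includes clinically significant changes in laboratory results in the safety evaluation, without defining them. SAP 6.2 says laboratory parameters were collected "both to be used to identify adverse events and for exploratory analyses", and that they will be summarised by treatment group and visit. Protocol 10.4 plans a descriptive comparison of abnormal laboratory results between treatment and placebo. Appendix A, section 2.1.1: "The respective reference ranges must be provided to the central study administration for uploading into the eCRF".

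**The concern.** Safety and tolerability at 1000, 2000 and 3000 mg per day is a stated objective, and the tables by arm and dose are where a reader will look for the answer. Two things should be clear from those tables: how many serious events occurred at each dose, and which events were eligible to be counted. As planned, neither is.

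Seriousness is not a table category, so a dose-level SAE count cannot be read off at all. Eligibility turns on a threshold that the protocol states in two ways. Laboratory safety is reported through a summary whose content is left open, although the protocol's own background section (KG7) raises a laboratory question, homocysteine and methylation capacity, for doses above 1000 mg.

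**Working it through.** There is no safety figure in the documents to reproduce, and no event rates from which to estimate a count. The check is to take each kind of event and follow it from the recording rules to the planned outputs.

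| Kind of event | Protocol 8.1.1 | Protocol 8.3 | Where it is recorded | SAP AE table by arm and dose |
|---|---|---|---|---|
| Non-serious, interferes with everyday life | Intensity 2-3 | Moderate or Severe | AE form | Has a row |
| Non-serious, needs medical intervention, no interference | Below intensity 2 | Moderate | Depends on which section was followed | Depends on the same choice |
| SAE of moderate or severe intensity | Intensity 2-3 | Moderate or Severe | AE registration and SAE pages | Has a row, not marked serious |
| SAE of mild intensity | Filtered out of AE registration | Mild | SAE pages (8.4.1) | No row |
| Abnormal laboratory value, no symptoms, no treatment | An AE by definition, filtered out | At most Mild | Laboratory data | No row |

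Three points follow.

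1. **Threshold.** The second row changes status according to the section applied. The rule decides what enters the only AE table, so the two sections have to be reconciled.

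2. **SAEs.** Section 8.4.1 first ties recording to section 8.1.1, which holds the filter, and then requires every SAE on the SAE pages. The second statement carries no intensity limit, so the better reading is that all SAEs are captured. The gap is therefore in the tabulation: row four is absent from the dose-level table and row three is present but unidentifiable as serious.

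3. **Laboratory values.** The flow chart in Appendix A, section 2, lists 22 routine parameters at all four visits (counting white cells with differential as one, and leaving out the pregnancy test, done at baseline only). AE recording starts after baseline (protocol 8.2), so three visits are relevant: 22 × 3 = 66 scheduled post-baseline values per participant, and 66 × 80 = 5,280 in the trial if all attend. This is the volume of data, not a number of abnormalities. SAP 6.2 plans no count of how many of these lie outside the reference range or moved there from baseline. It does present them by group and visit. In the DE-group, weeks 4, 8 and 12 close the 1000, 2000 and 3000 mg periods (protocol section 2), so that summary is in effect by dose.

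**The case against.** The strongest reply is that little is actually hidden.

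- **SAEs are not lost.** Protocol 8.4.1 sends every SAE to the SAE pages and 8.5 has SAEs discussed in the study report. Most of the seriousness criteria in 8.1.2, such as life-threatening events or persistent disability, would ordinarily be graded Moderate or Severe, so mild SAEs should be few. This stands. A reader might infer that mild SAEs disappear from the trial's results; the documents do not support that. But a discussion is not a count by arm and dose, and the lack of a serious category affects moderate and severe SAEs too.

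- **Laboratory results are part of the safety evaluation.** A reader might infer that laboratory toxicity is left out of the dose-safety results. It is not: SAP section 6 names laboratory results, SAP 6.2 summarises them by group and visit, and protocol 10.4 plans a comparison of abnormal results. Laboratory values can also still lead to a registered AE when there are interfering symptoms or, under 8.3, when intervention is needed. What remains is narrower: the SAP does not say how abnormal or clinically significant is defined, nor how many participants were affected.

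- **The homocysteine question is well covered.** Homocysteine, folic acid and methylmalonic acid are measured at every visit, and methyl donors and one-carbon metabolism have their own exploratory analyses. The KG7 concern is therefore not concealed by the AE filter. It only shows why a per-participant laboratory count is useful here.

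- **The filter is the protocol's rule, and recording is probably over.** The protocol estimates the last patient's completion at 22 April 2025; protocol 3.1 is dated 5 June 2025 and the SAP 16 June 2025. New wording cannot recover events that were never recorded. This stands, and it moves the useful change to the tables and to a statement of what was done.

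**Conclusion.** The point holds as a gap in specification and tabulation. The SAP plans no SAE table, its AE tables cannot show a mild SAE or identify any SAE as serious, and its laboratory summary does not deliver a defined comparison of abnormal results. The protocol's two thresholds for Moderate conflict and need to be reconciled.

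Its size cannot be computed: the documents give no rates for SAEs, for events needing intervention without interference, or for out-of-range values. The conclusion rests on two readings: that the requirement to document every SAE overrides the intensity filter, and that SAP 6.1 and 6.2 are the full list of planned safety outputs for AEs and laboratory data. If the first reading is wrong, the SAE gap is wider than described here. No efficacy analysis is affected.

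**What to change.** - **SAP 6.1:** add a table and a listing of all SAEs, whatever their intensity, by arm and by dose level at onset.
- **SAP 6.2:** add counts or shift tables (within or outside the reference range, baseline to each visit) by arm and visit or dose, using the reference ranges that Appendix A requires to be provided. State that these tables are the comparison of abnormal results foreseen in protocol 10.4, and define clinically significant as used in SAP section 6.
- **Protocol 8.1.1, 8.3 and 8.4.1:** reconcile the two descriptions of intensity 2, and state that SAEs are outside the intensity filter.
- **If recording is already complete:** report which threshold the investigators actually applied, so that the AE counts can be interpreted.

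The cost is two or three descriptive outputs from existing data, plus wording. No new data collection is needed.

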### 6.1 Adverse Events

#### 6.1.1 Descriptive Statistics

The frequency and severity of adverse events (AE) will be presented in tabular format between all three randomization groups and NR dose levels (1000 mg, 2000 mg and 3000 mg). AEs are evaluated as being either unrelated, unlikely, possible, probable or definite in relation to the investigational medicinal product (IMP). AEs will be grouped by status; Moderate or Severe and grouped by relation to the IMP. AEs will be presented by number and by percentage of group. The safety analysis set (SAS) will be used for analysis. The variables are continuous. No further statistical testing will be performed on the AEs. We refer the reader to the study protocol for a more detailed definition of AE severity and registration procedures.

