# N-DOSE Protocol v3.1

	one-carbon metabolism in PD at week 12.	
	To assess the dose-response relationship between NR dose (1000 mg, 2000 mg, 3000 mg per day) and changes in folate and one-carbon metabolism in PD from baseline to weeks 4, 8 and 12.	Change in folate and one-carbon metabolites in blood, measured by HPLC-MS.
	To compare the effect of orally administered NR in the DE-group versus DS-group on methyl donors in PD at week 12.	Change in methyl-donors (e.g., SAM), measured by HPLC-MS, in the blood and/or CSF.
	To assess the dose-response relationship between NR dose (1000 mg, 2000 mg, 3000 mg per day) and changes in methyl-donors in PD from baseline to weeks 4, 8 and 12.	Change in methyl-donors (e.g., SAM), measured by HPLC-MS, in the blood.
	To compare the effect of orally administered NR in the DE-group versus DS-group on DNA methylation at week 12.	Change in level and genomic distribution of DNA methylation, measured by Illumina Infinium MethylationEpic kit.
	To assess the dose-response relationship between NR dose (1000 mg, 2000 mg, 3000 mg per day) and changes in methyl-donors in PD from baseline to weeks 4, 8 and 12.	Change in level and genomic distribution of DNA methylation, measured by Illumina Infinium MethylationEpic kit.
	To compare the effect of orally administered NR in the DE-group versus DS-group on synthesis of neurotransmitters in CSF at week 12.	Change in neurotransmitters in CSF, measured by HPLC-MS.
	Determine whether NR-therapy affects the gut microbiome in a dose-responsive manner at week 12.	Change in gut microbiome composition, measured by metagenomics in fecal samples.
	To compare the effect of orally administered NR in the DE-group versus DS-group on the gut metabolome at week 12.	Change in fecal metabolomics, measured by LC-MS in fecal samples.
	To compare the effect of orally administered NR in the DE-group versus DS-group on the sense of smell at week 12.	Change in sense of smell, measured by B-SIT score.
Safety	To determine the safety and tolerability of NR at a dose of 1000 mg, 2000 mg, and 3000 mg per day in PD.	Number and severity of adverse events from baseline to week 12 across treatment groups and NR dose levels.

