## 1.4 Rationale for the Study and Purpose

Our phase I trials (see section 1.3) showed that NR holds promise as a potential neuroprotective, disease-modifying therapy for PD, and that its effects are likely to be dose-dependent. Encouraged by these findings, this project aims to determine the optimal biological dose of NR in PD and to further explore its neuroprotective potential. The outcomes of this project will take us several steps closer to developing NR into a PD-drug, so that we may harness its full therapeutic potential and maximize its clinical benefit and impact. Specifically, the following knowledge gaps (KG) will be addressed by the N-DOSE study:

**KG1 – Determine the Optimal Biological Dose (OBD) of NR in PD.** We define the OBD of NR as the dose required to achieve maximal cerebral NAD increase (measured by P-MRS or CSF metabolomics), or maximal expression increase in the NRRP (measured by FDG-PET), or maximal proportion of MRS-responders, in the absence of unacceptable toxicity.

While our trials show that the treatment responses to NR in PD are clearly dose-dependent, the OBD of NR in PD remains undetermined. Based on the results of NR-SAFE, it is likely that improved biological and clinical responses can be achieved by escalating the dose. Moreover, the NR OBD may not be universal. NADPARK showed that the NR-mediated increase in cerebral NAD-levels, and accompanying metabolic and clinical response, are not universal and vary across individuals. The fact that all NR-recipients showed a robust metabolic response in blood, muscle and CSF, suggests that the variable cerebral NAD response may reflect interindividual variability in cerebral NAD metabolism (i.e., variation in the rate of NAD-synthesis or consumption). It is likely that such differences can be modulated by varying the substrate concentration (i.e., the intake dose of NR). This question is critical to address, so that NR-therapy can be correctly dosed and tailored to individual patients to achieve an optimal neurometabolic response.

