### 1.2 Intervention(s)

#### 1.2.1 Brief description of the study intervention(s)

**Dose-escalation group (DE-group):** This group consists of 40 persons with Parkinson's disease who will receive an escalating dose of NR over three months: month one NR 1000 mg daily, month two NR 2000 mg daily, month three NR 3000 mg daily.

**Dose-stable group (DS-group):** This group consists of 20 persons with Parkinson's disease who will receive a dose of NR 1000 mg daily for three months.

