**Safety**

N/A	Number and severity of adverse events between treatment groups and study visits.	During trial	Continuous
-----	--	--------------	------------

---

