### 6.3 Vital Signs

Changes in vital signs (including systolic and diastolic blood pressure (mmHg), heart rate (beats per minute) and weight (kg)) will be summarised by treatment group and visit.

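### The adverse-event table by NR dose level has no defined denominator and no person-time, so on two possible readings 2000 and 3000 mg would look safer through shorter exposure alone

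*SAP*

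**What the plan says.** SAP 6.1.1 presents AE frequency and severity "between all three randomization groups and NR dose levels (1000 mg, 2000 mg and 3000 mg"), using the safety set and without testing. The metric is: "AEs will be presented by number and by percentage of group".

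SAP 4.5 describes the safety endpoint differently: "Number and severity of adverse events between treatment groups and study visits". The SAP uses the same axis for its other safety data. Under 6.2, "Clinical laboratory parameters will be summarised by treatment group and visit", and under 6.3 vital signs "will be summarised by treatment group and visit". Only 6.1.1, which specifies the AE tables, leaves out the visit.

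The dose-level wording comes from the protocol. The safety endpoint in its synopsis and section 2 is "Number and severity of adverse events from baseline to week 12 across treatment groups and NR dose levels". SAP 1.2.1 gives the DE schedule as "month one NR 1000 mg daily, month two NR 2000 mg daily, month three NR 3000 mg daily", and DS stays on 1000 mg daily for three months.

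Neither document gives an exposure denominator, a pooling rule for 1000 mg, or a rule for assigning an AE to a dose level.

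**The concern.** Number and percentage are fair summaries when the columns have similar time at risk. Here they may not. A person in DS can accumulate AEs at 1000 mg for three times as long as a person in DE can at 2000 or 3000 mg. Two layouts that 6.1.1 permits would put unequal exposure side by side:

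- **Pooled reading:** the 1000 mg level includes everyone who took 1000 mg, that is, DS over 12 weeks plus DE over weeks 0-4.
- **Separate reading:** each 4-week DE dose level is shown beside 12-week DS and placebo columns.

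In both, equal AE rates produce lower figures at the two higher doses. Safety at each of the three doses is a stated objective, and Protocol 1.4 defines the optimal biological dose as one reached "in the absence of unacceptable toxicity". The table is therefore likely to be read as evidence on dose and safety.

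**Working it through.** The plan states no AE rate, expected count or exposure total, so there is no figure of its own to reproduce.

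**Inputs.** Group sizes are placebo 20, DS 20 and DE 40 (Protocol 4.2). Planned time is 12 weeks on placebo or in DS, and 4 weeks at each DE dose (Protocol 2; SAP 1.2).

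**Planned person-weeks = people × weeks**

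- Placebo, and likewise DS: 20 × 12 = 240 in 20 people, or 12 weeks per person.
- Each DE dose level: 40 × 4 = 160 in 40 people, or 4 weeks per person.
- 1000 mg with DS and DE pooled: 240 + 160 = 400 in 60 people, or 400/60 = 6.67 weeks per person.

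**Events per person at any equal constant rate**

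- Pooled 1000 mg against 2000 or 3000 mg: 6.67/4 = 1.67.
- DS or placebo against a DE level: 12/4 = 3.

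The 30-day periods in Protocol 3.1 scale every level alike and leave these ratios unchanged.

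**People with at least one AE.** If this is what the percentage means, it equals 1 − exp(−rate × weeks), and the pooled value is (20 × 12-week value + 40 × 4-week value)/60. The rates below are assumptions, since the documents give none.

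| Assumed AEs per person-week | 4-week DE level | Pooled 1000 mg | 12-week DS or placebo | Pooled ÷ level | DS ÷ level |
|---|---|---|---|---|---|
| 0.02 | 8% | 12% | 21% | 1.59 | 2.78 |
| 0.05 | 18% | 27% | 45% | 1.50 | 2.49 |
| 0.10 | 33% | 45% | 70% | 1.37 | 2.12 |

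**What could be hidden.** Take 0.05 per person-week and a true 1.5-fold rate at 3000 mg. The 3000 mg level then shows 1 − exp(−0.075 × 4) = 26%. That looks no worse than pooled 1000 mg (27%) and better than 12-week DS (45%). Against DS or placebo over the same 4 weeks (18%) the excess is visible.

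**After the fix.** With person-time, equal rates give equal figures: at 0.05, every level shows 5 AEs per 100 person-weeks. With matched 4-week periods, every cell shows 18%.

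**Precision.** Seven of 40 people (about 18%) has a 95% Wilson interval of 9-32%. The change corrects the direction of the comparison and adds no power.

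**The case against.** The strongest reply is that the SAP already lists the right table. AEs are registered at visits 2, 3 and 4, and the DE dose changes at those visits. AEs by treatment group and study visit, as in 4.5, therefore already means three 4-week periods by placebo, DS and DE. This largely stands: much of the fix is reconciling 4.5 with 6.1.1. But 6.1.1 is the section that specifies the tables, and it names dose level instead of visit.

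A reader might infer that the plan pools DS and DE at 1000 mg, or that its safety analysis is biased towards the higher doses. The documents do not support either. The groups that the SAP defines are DE, DS and placebo, and 6.1.1 can be read as randomised group crossed with dose level, which pools nothing. Setting a 4-week DE row against a 12-week column would also be the reader's own contrast, because the durations are stated. What stands is that dose level is named without a denominator, so the unequal layouts are not excluded.

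The ratios also assume a constant rate. If AEs cluster after the first dose whatever its size, the ratio of 12-week DS to DE weeks 0-4 falls below 3, while the ratio to DE weeks 8-12 rises above it. The figure of 3 is thus an illustration and not a bound.

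Finally, Protocol 8.2 records AEs until 7 days after the last visit, but the endpoint runs from baseline to week 12 and nothing assigns those late events to a dose. Only if they were attributed to the last dose would the events-per-person ratios against 3000 mg become (20 × 13 + 40 × 4)/60 ÷ 5 = 1.40 and 13/5 = 2.6. Within DE, 3000 mg would then have 5 weeks against 4.

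**Conclusion.** The concern holds as a reporting ambiguity with a predictable direction. If 1000 mg pools DS and DE, or a 4-week DE level is read against 12-week DS or placebo, the higher doses look safer by factors of 1.67 or 3 in events per person. The factors are smaller for people with at least one AE. These sizes rest on equal constant rates, full retention and counting each AE at the dose of onset.

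Two comparisons are not affected: the three randomised groups over 12 weeks, and the planned 4-week levels within DE if the 7-day tail is kept apart. The consequence is modest. There is no test, no numerical toxicity rule and no decision that depends on the table, and counts per level will be small. It is still worth correcting before the tables are produced, because safety by dose is an objective and the remedy is cheap.

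**What to change.** Amend SAP 6.1.1 so that it agrees with 4.5:

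- Make the dose-level AE table one of 4-week period (0-4, 4-8, 8-12) by randomised group (placebo, DS, DE), with each AE assigned by onset date. DE at 2000 and 3000 mg is then compared with concurrent DS and placebo over equal time.
- In any table pooled by dose, use as denominator the people who received that dose, so that those who left earlier do not dilute it. State whether DS and DE are pooled, and add person-weeks and AEs per 100 person-weeks. Note that person-time does not remove the confounding of dose with period within DE.
- State whether percentage means people with at least one AE.
- Show AEs in the 7 days after the last visit separately.
- Keep number and percentage for the 12-week comparison of the three randomised groups.

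The cost is one or two extra descriptive tables with small cells. No new data are needed: onset dates are recorded under Protocol 8.3, and SAP 3.4.1 already uses treatment duration per dispensation.
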